Outcome measures: Venous patency, blood flow direction, peak reflux velocity, circumferences (C1, C2) at the end of each segment length (L), BMI, VRT, Genomic DNA blood test, Estriol (E3) levels, progesterone serum levels, outcome of quality of life.

Population: 70 Random pregnant women.

Eligibility: Pregnant women aged between 18-47 years old.

Duration: 1 year, follow up period will be conducted at the end of first, second and third trimester and three months after giving birth.

1 Introduction

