3.3.2 Protocol for Duplex ultrasound scan (DUS)

All recruited pregnant women be scanned by duplex ultrasound scan (DUS) to investigate the evidence of VV. The examination will be bi lateral for each patient. The patient will be asked to remove their clothes to expose the lower limb from groin to ankle. Patient will be examined standing to evaluate valves competency against gravity. This is because veins are more dilated while standing which make it easier and more accurate to assess. This examination is considered intimate; therefore, a chaperone will be offered. The scan duration will take 30-45 min and patients may sometimes feel dizzy during the examination. To overcome this issue, patients will be asked to sit and take a rest during the examination.

There are two main techniques which will be applied to all venous segments. Firstly, B mode technique. B mode technique will be used to evaluate vein patency in transverse scan plane by observing the compressibility of veins to rule out any possibility of blood clots. Secondly, Spectral (Pulse wave) doppler technique will be used to evaluate venous flow characteristics (phasicity, spontaneity and direction flow) in longitudinal scan plane by applying manual distal augmentation to assess the reflux duration. All scans and measurements will be performed on SuperSonic Imagine's Aixplorer ® ultrasound system. Following this, 9 MHz linear ultrasound probe will be placed on the patient skin over the venous blood vessel to be scanned, with the use of coupling gel between the skin and the probe.

The scan will start by evaluating the deep and superficial veins system. Firstly, deep veins will be assessed by scanning the Common femoral vein (CFV) at the groin for patency and flow. Any abnormality in CFV indicates iliac vein obstruction therefore iliac veins and inferior vena cava should be examined. The examination will be continued by scanning the length of femoral vein (FV) (proximal to distal), popliteal vein and calf veins. Any thrombus or incompetence (Incompetent veins are defined as a reflux time more than 0.5 seconds) will be recorded.

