3.3.5 Protocol for Iliac vein compression test (venous outflow function)

This proposed study will examine iliac vein compression (venous outflow function) in pregnancy using photoplethysmography (PPG) technique. This is due to the difficulty of examining iliac veins using ultrasound in pregnancy due to increased size of gravid uterus. Large size of gravid uterus in pregnancy causes iliac veins compression which makes iliac veins hard to investigate. PPG is a non-invasive method used to evaluate the severity venous reflux by measuring the venous refilling time (VRT). VRT is considered to be abnormal when the refilling time is measured (less than 20 seconds). PPG technique has low specificity compared to other imaging tests and it is considered not accurate in locating the areas of reflux. However, alongside with its capability of evaluating the degree of reflux, it can also predict the treatment outcomes (Cheng and Wong, 1995).

The principal of PPG works by using a small light source and a photoelectric cell attached to the skin. Produced light will transmit the skin and will be scattered by the tissue and partially absorbed. Scattered light will emerge out passing the skin to be detected by photoelectric cell. Photoelectric cell will be attached on the side or opposite the source of light to monitor blood perfusion based on transmission and reflection modes. Following this, the intensity of the light signals detected by photoelectric cell will be converted to PPG signals.

In this proposed study, patient will be seated with her both legs dangling on the floor. PPG sensor will be attached to the patient's skin in the medial supramalleolar area of the leg (the distal lower medial area of the leg). The exam will start by asking the patient to flex and extend one foot (five times), while the other foot placed on the floor.

Following this, a traced graph will appear on the machine's screen. When the trace is stable, it means that it is the end of the VRT. The exam will be repeated to evaluate the filling time of the second leg. All measurements will be recorded immediately.

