5.2.2 Serious AEs

An SAE form should be completed and faxed to the Chief Investigator within 24 hours. However, death due to eclampsia and any health complications worsened during pregnancy does not need reporting as SAEs.

All SAEs should be reported to **the North of Scotland Research Ethics Committee** where in the opinion of the Chief Investigator, the event was:

- 'related', ie resulted from the administration of any of the research procedures; and

- 'unexpected', ie an event that is not listed in the protocol as an expected occurrence

Reports of related and unexpected SAEs should be submitted within 15 days of the Chief Investigator becoming aware of the event, using the NRES SAE form for non-IMP studies. The Chief Investigator must also notify the Sponsor of all SAEs.

Local investigators should report any SAEs as required by their Local Research Ethics Committee, Sponsor and/or Research & Development Office.

Contact details for reporting SAEs

[contact]

[contact]

[contact] attention [name]

[contact] (Mon to Fri 09.00 – 17.00)

6 Incidental findings:

A lay summary of aggregated results will be provided to all participants. If there is an incidental finding such as DVT, which likely have a major impact on patient's medical management then the doctor treating her will be informed and participant will be removed/ withdrawn from the study.

7 Assessment and follow up

All previously mentioned interventions and procedures including (DUS, VFI, Truncated cone tool, PPG, hormonal blood test, AVVQ questionnaire) will be performed four times (in first, second, third trimester once and three months after giving birth). DNA genomic blood test will be performed once only in the first trimester of pregnancy. No

further follow-up required after this time point. The study expected time for each participant is 12 months in total.

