8.2 Analysis plan

All analyses will be performed based on the intention of follow-up. The analysis population will include all participants enrolled in the study, including those who developed varicose veins during pregnancy and those who do not.

Analysis of primary and secondary outcomes:

Venous patency and Peak reflux time recordings from VFI scan will be correlated with Venous patency and peak reflux time recordings from DUS scan. This will be performed using descriptive summary statistics. Mixed multivariable logistic regression will be used to model venous patency and peak reflux velocity in each scan.

Secondary outcome which include measuring the circumferences (C1, C2) and length of segments (h) using Truncated cone method. Calculated volume will be determined by summing segment volumes derived from the truncated cone formula. Pearson product moment correlations, paired t tests, and linear regression tests will be used to assess relative association and absolute differences between calculated volumes in each follow up.

Secondary outcome which include PPG will be analysed by comparing the mean value for the venous refilling time (VRT) by Student's *t* test, agreement between DUS and PPG classification was expressed as a kappa (**K**) value.

Genomic DNA blood samples results will be correlated with the UK biobank study. Test statistics will be used to identify genetic variants that influence varicose vein susceptibility.

Each hormonal blood samples results including Estroil (E3) and progesterone serum levels will be correlated with the results of the next follow up to provide comprehensive information about increased hormonal levels in pregnancy and varicose veins development.

Outcome of quality of life statistical analysis will be performed using the Statistical Package for the Social Sciences (SPSS 23.0) for Windows. Evaluation of AVVQ consisted of quality of life in first trimester, second trimester, third trimester and three months after giving birth will be done using the Friedman test.

8.3 Data analysis:

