The data obtained will be subjected to statistical analysis by an independent biostatistician. SPSS Version 23.0 or/ and STATA Version 10.0 will be used for statistical analysis. Measures such as the mean and standard deviation or median and interquartile range will be used to summarise continuous variables such as age and BMI. Tables reporting the numbers and percentages will be used for categorical variables such as varicose veins and smoking. Chi square or Fisher's exact test will be used to compare categorical variables such as varicose veins and smoking at the final trimester. The t-test or Mann-Whitney test will be used to compare continuous variables such as age with varicose veins at the final trimester. The paired t-test or Wilcoxon signed-rank test will be used to compare BMI between first and third trimester. The Kappa statistic will be used to compare DUS and VFI regarding direction and velocity. Longitudinal analysis will be used to look at factors associated with varicose veins. Factors include age, BMI, smoking, ethnicity, pregnancies and family history. A significance value (p-value) less than 0.05 is considered statistically significant.

9 Regulatory issues

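### For the DUS–PPG classification section 8.2 names only kappa, which moves with reflux prevalence and cannot separate PPG's false positives from its false negatives

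*Combined protocol and SAP*

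**What the plan says.** Section 8.2 gives PPG two analyses in one sentence. The first is a Student's t test "comparing the mean value for the venous refilling time (VRT"), without saying which groups or visits are compared. The second is for the classification: "agreement between DUS and PPG classification was expressed as a kappa". No other statistic is named for DUS against PPG in 8.2 or 8.3.

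The two classes are set in the methods. For PPG (3.3.5), "VRT is considered to be abnormal when the refilling time is measured (less than 20 seconds"). For DUS (3.3.2), "Incompetent veins are defined as a reflux time more than 0.5 seconds". Section 3.3.5 also states that "PPG technique has low specificity compared to other imaging tests". Section 7.2 places DUS as the primary outcome procedure and PPG among the secondary ones. Section 7 says the procedures "will be performed four times (in first, second, third trimester once and three months after giving birth"). The Study summary gives the cohort as "70 Random pregnant women".

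Section 8.3 uses kappa once more, for another pair of methods: "The Kappa statistic will be used to compare DUS and VFI regarding direction and velocity".

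The plan does not say whether the DUS–PPG kappa is computed per visit or pooled, or per leg or per woman.

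**The concern.** Kappa is made for two interchangeable raters. Here the protocol defines incompetence by DUS and names the weak point of PPG in advance. The natural question is therefore how many refluxing legs PPG finds and how many non-refluxing legs it flags. Kappa answers neither, because it folds both errors into one number.

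Kappa also depends on the proportion with reflux. This study follows the development of varicose veins over four visits, so that proportion may well change. A kappa from this cohort then reflects its case mix as well as the performance of PPG, and it does not carry over to a group with a different prevalence.

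What is at stake is the reading of one secondary comparison: whether VRT below 20 s is a usable stand-in for DUS reflux and, if not, which way it fails.

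**Working it through.** **The plan's own figures.** None is given for kappa, PPG accuracy or reflux prevalence. The only design figure is the 91.27% power in 8.1. It reproduces: with 70 women and a null proportion of 0.25, the lower rejection region is 10 or fewer events, and the probability of that at 0.10 is 0.9127. It has no bearing on this point.

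**Inputs.** The cut-offs are those of 3.3.5 and 3.3.2. Sensitivity (Se), specificity (Sp) and DUS reflux prevalence (p) are my assumptions. The values 10% and 25% are borrowed from 8.1 as illustrations only, since 8.1 does not define its event.

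**Formulas.**
- observed agreement: po = p·Se + (1−p)·Sp
- proportion PPG-positive: q = p·Se + (1−p)(1−Sp)
- chance agreement: pe = p·q + (1−p)(1−q)
- kappa = (po − pe)/(1 − pe)

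**Step 1: prevalence.** For Se 0.90 and Sp 0.60:
- p = 0.10: po = 0.630, q = 0.450, pe = 0.540, kappa = 0.090/0.460 = 0.20
- p = 0.25: po = 0.675, q = 0.525, pe = 0.4875, kappa = 0.1875/0.5125 = 0.37

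| Assumed Se/Sp | kappa at p = 10% | kappa at p = 25% | rise |
|---|---|---|---|
| 90/50 | 0.14 | 0.27 | 0.14 |
| 90/60 | 0.20 | 0.37 | 0.17 |
| 85/70 | 0.26 | 0.44 | 0.18 |
| 90/70 | 0.28 | 0.47 | 0.20 |
| 90/80 | 0.40 | 0.60 | 0.20 |

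Rises are taken before rounding. Sensitivity and specificity are constant along each row.

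Pooling the visits does not remove the dependence. If half the observations came at 10% and half at 25%, the pooled p is 0.175. At 90/60 that gives po = 0.6525, q = 0.4875, pe = 0.5081 and kappa = 0.1444/0.4919 = 0.29, a value set by the mix.

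The effect is not universal. At 60/90 (low sensitivity, high specificity) kappa is nearly flat above 20% prevalence: 0.50 at 20%, 0.52 at 25% and 40%, and 0.50 at 50%. That pattern is the reverse of the weakness described in 3.3.5.

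**Step 2: which error.** At p = 0.25, a kappa of about 0.37 arises from each of these Se/Sp pairs: 90/60, 74/70, 59/80 and 43/90. The first flags 40% of non-refluxing legs. The last misses 57% of refluxing ones.

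**Step 3: sampling error.** Simulating 70 independent women at 90/60, the standard deviation of kappa is 0.081 at 10% prevalence and 0.093 at 25%. The standard error of a difference between two such visits, treated as independent, is √(0.081² + 0.093²) = 0.12, so the shift of 0.17 is about 1.4 standard errors. At 90/80 it is 0.20 against 0.16, about 1.3. With 140 legs treated as independent the ratio is 1.8 to 2.0, but two legs of one woman are not independent.

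**Step 4: precision of the alternative.** One observation per woman, normal approximation:
- 10% prevalence (7 DUS-positive, 63 negative): Se 0.90 ± 1.96√(0.09/7) = ±0.22; Sp 0.60 ± 1.96√(0.24/63) = ±0.12
- 25% prevalence (18 positive, 52 negative): Se ±0.14; Sp ±0.13

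**The case against.** **The table could be rebuilt.** Section 8.3 promises counts and percentages for categorical variables. If the DUS and PPG classes were tabulated on the same units, the two margins and kappa would determine the 2x2 table. The four pairs in step 2 have PPG-positive proportions of 52.5%, 41%, 30% and 18%, so they would be told apart. The algebra is right, but 8.3 gives varicose veins and smoking as its examples and does not commit to tabulating PPG classes, let alone on matching units.

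**DUS may not be the right reference.** Section 3.3.5 brings PPG in as an outflow test because the iliac veins are hard to image in pregnancy. Discordance with leg DUS might then be extra information and not error. This has some force. But 3.3.5 and 7.2 also describe VRT as a measure of reflux severity, and 8.2 itself sets the PPG class against DUS.

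**Stronger readings that the documents do not support.**
- A reader might infer that PPG will appear to change by trimester. The plan does not say that kappa is computed or compared by visit. Fixed accuracy throughout pregnancy is also an assumption, and at this size the shift is only 1.3 to 1.4 standard errors.
- A reader might infer that the measured seconds are thrown away. They are not: the t test uses mean VRT, although its groups are unstated.
- A reader might infer that low specificity is concealed. Section 3.3.5 states it openly, and low specificity does lower kappa. It simply cannot be distinguished from low sensitivity there.
- A reader might infer that the antenatal test of section 2 is compromised. PPG is not named as that test, and same-visit accuracy against DUS would not measure prediction of post-partum varicose veins either.

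**Conclusion.** The point stands as an improvement to a secondary analysis. Kappa alone cannot show the weakness that the protocol itself attributes to PPG, and its value depends on prevalence whether it is computed by visit or pooled. Over the assumed low-to-moderate specificities (50% to 80%) with sensitivity of 85% to 90%, a move from 10% to 25% prevalence raises kappa by 0.14 to 0.20 with no change in accuracy. These sizes rest entirely on assumed accuracy and prevalence, since the documents give neither. That kappa merges the two errors does not depend on those assumptions.

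The primary outcome and the sample size are unaffected. For DUS against VFI flow direction in 8.3, kappa has the same property. How much it matters there depends on the antegrade–retrograde split, which the documents do not give.

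**What to change.** In 8.2:
- State a per-leg DUS reflux definition in advance: either any assessed segment over 0.5 s, or a named list of segments. Sections 3.3.2 and 7.2 give no rule for combining deep, superficial and perforating veins into one leg-level class.
- Report the DUS-by-PPG 2x2 table, with sensitivity and specificity of VRT below 20 s against that definition. Use 95% intervals that allow for two legs and repeated visits per woman, such as a cluster bootstrap by woman.
- Give pooled estimates as the main result and by-visit figures as descriptive. Add the area under the ROC curve for VRT in seconds, pooled across visits.
- Name the groups for the t test on VRT.
- Keep kappa as a supporting figure, and state its unit and visit.

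In 8.3, for DUS against VFI direction, report positive (retrograde) and negative (antegrade) agreement beside kappa.

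The cost is SAP wording and a little more analysis on data already planned. The drawback is imprecision: with about 7 DUS-positive women at a visit, sensitivity is known only to about ±0.22, which is why by-visit figures should stay descriptive. The report should also say that these figures describe PPG against DUS at the same visit and not prediction of post-partum disease.

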3.3.6 Protocol for blood tests (genomic and hormonal blood tests)

Genetic risk factors are reported to play an important role in the aetiology of varicose veins. In this proposed study, we aim to estimate the heritability of varicose veins among recruited pregnant women by taking a 30-ml blood sample for genomic DNA testing. This will be performed once in the first trimester. Results will be entered to the research database for analysis and correlation with the UK bio bank study (Fukaya *et al.*, 2018).

Along with the genomic blood samples, hormonal blood samples will be taken from patients in each trimester and three months after giving birth. This is because elevated estrogen and progesterone hormones levels were linked to VV development (Mashiah *et al.*, 1991; Ortega, Asunsolo, Leal, *et al.*, 2018). Progesterone serum blood test will be conducted to evaluate the progesterone levels during pregnancy and correlate the result with the incidence of VV. Normal progesterone serum levels varies according to the trimester of pregnancy. For instance, according to the NHS, progesterone levels in the first trimester estimates between 6.9 to 470 nmol/L, 71.6 to 300 nmol/L in the second trimester and 88 to 770 nmol/L in the third trimester. Therefore, progesterone hormone reaches the highest levels in the third trimester which suggests the potential effect of this hormone on venous pathology in late pregnancy.

In addition, estrogen hormone blood test will be tested to associate the effect of estrogen with VV incidence. Estrogen hormone has three main types which are estrone, estradiol and Estriol and each type has different function. Estrone (E1) is the main hormone in females which is found after menopause. Estradiol (E2) is a female hormone found in non-pregnant women and involved in regulating menstrual cycles. Estriol (E3) is a type of estrogen hormone produced with higher amounts in pregnancy. This proposed study will investigate Estriol (E3) and progesterone serum blood test in each follow up which include first, second, third trimesters and three months after

giving birth in order to correlate hormonal changes with any potential venous pathology incidence.

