8.1 Sample size

An exact binomial test with a nominal 5% two-sided significance level will have 91.27% power to detect the difference between the null hypothesis proportion, π_0 of 0.25 and the Alternative proportion, π_1 , of 0.1 when the sample size is **70**.

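### With one DNA sample from each of at most 70 women, the study can neither estimate heritability nor identify susceptibility variants, and the genetic analysis has no variant list or error control

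*Combined protocol and SAP*

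**What the plan says.** Two genetic aims appear. In section 3.3.6: "we aim to estimate the heritability of varicose veins among recruited pregnant women by taking a 30-ml blood sample for genomic DNA testing". In section 8.2, after a sentence saying that the DNA results will be correlated with the UK Biobank study: "Test statistics will be used to identify genetic variants that influence varicose vein susceptibility". Section 7.2 lists genomic DNA among the secondary outcomes.

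The data behind both aims are limited. The study summary gives "Population: 70 Random pregnant women", and section 7 says "DNA genomic blood test will be performed once only in the first trimester of pregnancy". Nothing provides for sampling relatives. The only significance rule closes section 8.3: "A significance value (p-value) less than 0.05 is considered statistically significant".

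The document gives no number or list of variants, genotyping method, genetic model, multiplicity rule, ancestry adjustment for the genetic tests, or heritability estimator. Section 8.1 justifies the sample size by a one-sample test of a proportion, which does not concern genetics.

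**The concern.** Heritability is estimated by comparing likeness in the trait with genetic relatedness. Without relatives, the only information is the small chance variation in genomic similarity between unrelated women, and 70 women supply very little of it.

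Variant identification needs enough cases to detect realistic effects and a threshold suited to the number of tests. The plan shows neither. A variant reported as significant under the general rule would carry little evidence, and a non-significant result would exclude almost nothing.

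The primary objective (section 2) is an antenatal test to predict post-partum VV, so a variant wrongly called identified could be carried into that test. The samples also go to a tissue bank for future research (3.3.6), where such a claim could be taken up again.

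**Working it through.** **The plan's own figure.** Section 8.1 states "An exact binomial test with a nominal 5% two-sided significance level will have 91.27% power" for a "null hypothesis proportion, π_0 of 0.25" against an "Alternative proportion, π_1 , of 0.1", with n = 70. The exact test with at most 0.025 in each tail rejects if X ≤ 10 or X ≥ 26. Its attained level is 0.0383 and its power at 0.10 is 91.27%. The figure reproduces, but says nothing about the genetic aims.

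**Inputs from the document.** n = 70, an upper limit because section 4.3 excludes women who miss later scans; one DNA sample per woman; threshold 0.05; proportions 0.10 and 0.25.

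**Assumptions not in the document.** Section 8.1 does not say what its proportions measure. Read as VV frequencies, they give 0.10 × 70 = 7 and 0.25 × 70 = 17.5, taken as 17 cases. Allele frequency 0.3, the odds ratios, the variant counts and the relatedness variance are also assumed.

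**Heritability.** For unrelated people, SE(h²) = √[2 / (n² × var A)], where var A is the variance of pairwise genomic relatedness. With n² = 4,900:

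| var A | SE(h²) | 1.96 × SE | n for SE = 0.10 |
|---|---|---|---|
| 1e-5 | √(2/0.049) = 6.4 | 12.5 | about 4,470 |
| 2e-5 | √(2/0.098) = 4.5 | 8.9 | about 3,160 |
| 4e-5 | √(2/0.196) = 3.2 | 6.3 | about 2,240 |

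Heritability lies between 0 and 1. In every row the 95% interval around any estimate in that range covers all of it. These are observed-scale values; on the liability scale the SE is larger, about 6 to 19.

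**Power for one variant.** The logistic noncentrality is λ = (ln OR)² × Var(G) × n × φ(1−φ), with φ the case fraction and Var(G) = 2 × 0.3 × 0.7 = 0.42. Power is Φ(√λ − 1.96) + Φ(−√λ − 1.96). The term nφ(1−φ) is 7 × 63/70 = 6.30 for 7 cases and 17 × 53/70 = 12.87 for 17.

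| OR | 7 cases: λ, power | 17 cases: λ, power |
|---|---|---|
| 1.2 | 0.088, 6% | 0.180, 7% |
| 1.5 | 0.435, 10% | 0.889, 16% |

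As a cross-check, comparing allele counts in cases and controls (7 and 17.5 cases, counting only the tail in the direction of the effect) gives 4-6% and 9-15%.

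**False hits.** Expected number = 0.05 × null variants: 1.5 for 30, 5 for 100, 25,000 for 500,000. The chance of at least one among 30 independent null tests is 1 − 0.95³⁰ = 79%.

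**Share of hits that are false.** With M variants tested, m of them real, the share is 0.05(M − m) / [0.05(M − m) + power × m].
- 1,000 tested, 30 real, power 10%: 48.5/(48.5 + 3) = 94%.
- 100 tested, 10 real, power 10%: 4.5/(4.5 + 1) = 82%.
- 30 tested, 10 real, power 7%: 1.0/(1.0 + 0.7) = 59%.
- 30 tested, all real: 0%.

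**Would a stricter threshold rescue it?** At 0.05/30 = 0.0017, power with 17 cases is 0.3% at OR 1.2 and 1.4% at OR 1.5. False hits are controlled, but almost nothing real would be found.

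**The case against.** The strongest objection is to a reading that the plan invites: that any hits would be mostly false. That does not follow from the document. It depends on how many variants are tested and how plausible they are beforehand, and neither is stated. The sentence just before the quoted one in section 8.2 links the DNA results to the UK Biobank study. If only a short list of established variants is to be checked, false hits need not dominate. This objection stands, and the mostly-false reading is limited to a broad panel or genome-wide scan. It does not rescue the aim, because power per variant is the same for a short list.

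A reader might also infer that p<0.05 was chosen as the rule for variant discovery. The rule closes a section that discusses demographic and clinical factors and does not mention genetics. It is fair only to say that no other rule is given.

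Third, the consequence is limited. The heritability aim is stated once, in 3.3.6, and is missing from the objectives, outcome table and analysis plan. Genomic DNA is one secondary outcome among several. This stands as to weight. A stated aim that the design cannot meet should still be removed.

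**Conclusion.** The point holds in two parts.

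The heritability aim cannot be met. The SE is about 3 to 6 over the assumed relatedness variances, several times the width of the whole possible range. No choice within that range changes the conclusion.

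The variant-identification aim is unsupported as written. Power per variant is 6-7% at OR 1.2 and 10-16% at OR 1.5 for 7 to 17 cases, given the assumed allele frequency and the reading of section 8.1's proportions as VV frequencies. The plan gives no variant list, genetic threshold or multiplicity rule. For a broad panel or genome-wide scan, hits would be mostly false; for a short list of established variants, the defect is very low power. The document does not settle which applies.

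This should be corrected, but it concerns a secondary outcome and leaves the primary DUS outcome untouched.

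**What to change.** - **Section 3.3.6:** delete the heritability aim.
- **Section 8.2:** replace the variant-identification sentence with a descriptive, exploratory analysis. Report estimates with 95% confidence intervals, make no p<0.05 claims for single variants, and call no variant identified.
- **Optional:** one pre-specified genetic risk score, tested once and labelled exploratory, reported as an odds ratio per SD with its 95% confidence interval. This requires the sponsor to confirm that the cited UK Biobank study supplies usable weights and that the assay covers those variants; the document shows neither. A single test keeps the error rate at 5%, but power remains limited. With Var = 1 in the formula above, it is 17% (7 cases) to 31% (17 cases) at OR 1.5 per SD, and 41% to 70% at OR 2.0 per SD. These odds ratios are assumptions.

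**Cost.** An amendment to protocol and SAP wording, which is more than an SAP edit because 3.3.6 is protocol text and section 9.1 records approvals as already obtained. The blood sample is unchanged. The optional score also depends on the genotyping assay, which is unspecified. The sponsor gives up discovery and heritability claims that the study could not have supported.
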